2.14. New York Heart Association class III (McMurray et al., 2012)

Classification of heart failure symptoms

Class I	People whose physical activity is not limited. Ordinary physical activity does not cause undue fatigue, heart palpitations, trouble breathing, or chest pain.
Class II	People who have some limitation on physical activity. They are comfortable at rest, but ordinary physical activity causes fatigue, heart palpitations, trouble breathing, or chest pain.
Class III	People who have a marked limitation on physical activity. They are comfortable at rest, but less-than-ordinary physical activity causes fatigue, heart palpitations, trouble breathing, or chest pain.
Class IV	People who are unable to carry on any physical activity without discomfort. Symptoms may be present even at rest. If any physical activity is done, discomfort increases.

2.15. 2017 Taiwan lipid guidelines for high-risk patients

LDL-C increased CV risk in patients with CKD. In adults with glomerular filtration rate (GFR) < 60 mL/min/1.73m² without chronic dialysis (CKD stage 3-5), statin therapy should be initiated if LDL-C ≥ 100 mg/dL. Ezetimibe can be added to a statin to consolidate the CV protection in CKD patients (Li et al., 2017)

3. Objective of the research

The target of this study is to focus on mechanisms underlying dyslipidemia in CKD and clinical trial evidence for lipid lowering therapy in patients with CKD via parameters of lipid, oxidative stress, tryptophan degradation as well as renal function, in comparison to statin/ezetimibe therapies in CKD patients with dyslipidemia.

- 1) To verify the effect of lipid lowering therapies on lipid profile and inflammatory status in Vietnamese CKD population. [Time Frame: at the baseline and at 4th month, and one-year following].
- 2) To compare the effect of lipid-lowering regimes (simvastatin mono-therapy and EZE/simvastatin 10/20, EZE /simvastatin 10/40 combination therapy) on lipid profile, oxidative stress indices, Tryptophan degradation, renal parameter, and side effect in Vietnamese CKD patient. [Time Frame: after the 4th month, 8th month and one-year following].

We hope with scientific evidence, doctors will well understand the mechanism, effect, and safety of potential and existing therapies. Therefore, the prescription rate of lipid-lowering drugs and control rate of hyperlipidemia could be increased in CKD

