4. METHODOLOGY

4.1. Study design: A prospectively study with clinical trials, 12 months follow up.

4.2. Subject: 30 patients with hypercholesterolemia (LDL-C), stage 3-4 Chronic Kidney Disease, not receiving dialysis and 30 control participants (sex, age-matched)

4.2.1. Inclusion Criteria:

30 patients with following criteria

- CKD in the 3,4 stage (e-GFR: 15-60 ml/min/1.73 m²)
- Presence of proteinuric CKD defined as creatinine clearance >20 ml/min/1.73 m² combined with urinary protein excretion rate >0.3 g/24 h
- LDL cholesterol concentration > 100 mg/dl (2,59 mmol/l)
- Age:
 - + ≥ 50 years old but not treated with chronic dialysis or kidney transplantation
 - + In adults aged 18-49 years with CKD but not treated with chronic dialysis or kidney transplantation, we suggest statin treatment in people with one or more of the following:
 - known coronary disease (myocardial infarction or coronary revascularization)
 - diabetes mellitus
 - prior ischemic stroke
 - estimated 10-year incidence of coronary death or non-fatal myocardial infarction > 10%

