4.6. Procedure

- Potentially eligible patients attended a screening visit in an internal examination room or internal department of Hue University Hospital for medical history and other eligibility criteria checked.

- Fasting blood samples will be taken for local laboratory assays lipid profile, proteinuria, urea and creatinine, creatine kinase, SGOT, SGPT, total blood count, total haemostasis test

- If the patient satisfies the including criteria, written informed consent obtained 30 enrolled patients will be randomized into 3 groups and will receive one of 3 lipid-lowering therapies at the baseline and continue for 12 months

Group 1: (10 participants) receive 40 mg/day simvastatin (patient No 1, 4, 7...)

Group 2: (10 participants) receive ezetimibe/simvastatin 10/20 mg/day: (patient No 2, 5, 8...)

Group 3: (10 participants) receive ezetimibe/simvastatin 10/40 mg/day: 10/40: (patient No 3, 6, 9...)

- Patients will follow the treatment for 12 months and will be seen in the study clinics for routine follow-up checks and blood test at 4, 8, and 12 months.

- At each follow-up time, study treatment will be continued, unexplained muscle pain and non-study treatment recorded.

Patients are asked for an unscheduled visit if they want to have any additional review.

- If patients are unable or unwilling to attend the follow-up checks, ask them if they have any serious adverse events.

- The blood samples will be sent to Biochemical Department of Sassari University for oxidative stress indices and Tryptophan degradation indices every 4 months.

5. Biochemical analysis

- Serum Creatinine, GFR, urine protein, lipid profile, SGOT, SGPT, CK (Total Cholesterol, LDL-C, HDL-C, TG): Will be done in Hue University hospital/Hue Central Hospital.

+ Total Cholesterol, LDL-C, HDL-C, and TG were measured by enzymatic methods using commercial kits (Boehringer-Mannheim, Mannheim, Germany): Patients must fast for at least 12 hours before the test

+ Serum CK levels were measured by using a fully automated biochemical analyzer (Abbot).

+ Proteinuria

+ Serum urea, creatinine

+ Total cells blood count

+ Total hemostasis test

[Time Frame: at baseline and 4, 8, 12 months of treatment]

- Serum concentrations of Oxidative stress indices (MDA, All/UA, Taurine), Trp degradation indices (Kyn, Trp, Kyn/Trp ratio): Will be done in Sassari University hospital.

MDA, All/UA ratio, taurine, Kyn, Trp were determined by capillary electrophoresis UV detection.

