STATISTICAL ANALYSIS PLAN

LIPID-LOWERING REGIMES IMPROVE OXIDATIVE STRESS, TRYPTOPHAN DEGRADATION IN HYPERCHOLESTEROLEMIA CKD PATIENTS

Date of review: 05th May, 2018

All results will be expressed as mean values (mean SD) or median values (median and range).

The statistical differences between the mean laboratory test results patients and control group will be analyzed by ANOVA one-way statistical analysis or by Student's t-test (with Kolmogorov-Smirnov for normality).

The statistical differences in the effect of each therapy on laboratory mean values will be evaluated by one way repeated measure ANOVA with Bonferroni correction or Dunnet T3 correction, if appropriate.

To compare the differences in the median values of laboratory tests between 3 groups, ANOVA one-way will be applied. If there are statistical differences between 3 groups, we will use deeply ANOVA one-way test to analyze which group is different from another group (with Bonferroni if Levene test ≥ 0.05 or Dunnet T3 if Levene test < 0.05).

Correlation analysis between variables will be performed by Pearson's correlation or Spearman's correlation as appropriate.

Statistical analysis will be performed by using SPSS for Windows, version 20.0 (IBM Corporation; Armonk, NY, USA).

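### The comparison of the three regimens is a one-way ANOVA that names no visit and makes no use of the baseline values the trial collects

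*SAP*

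**What the plan says.** Protocol section 3, objective 2, sets the comparison of the regimens at three times: "Time Frame: after the 4th month, 8th month and one-year following". Section 4.1 fixes the length of the study: "A prospectively study with clinical trials, 12 months follow up". Section 4.6 puts 10 patients in each arm, assigned by patient number: "Group 1: (10 participants) receive 40 mg/day simvastatin (patient No 1, 4, 7". Section 5 gives one schedule twice, for the local laboratory tests (lipids, renal and safety markers) and for the oxidative-stress and tryptophan indices: "Time Frame: at baseline and 4, 8, 12 months of treatment". Only total genome DNA methylation is listed without a time frame.

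For the comparison of the three arms the SAP says: "To compare the differences in the median values of laboratory tests between 3 groups, ANOVA one-way will be applied". If that test is significant, pairwise tests follow, "with Bonferroni if Levene test ≥ 0.05 or Dunnet T3 if Levene test < 0.05". One other sentence deals with repeated measurements: "effect of each therapy on laboratory mean values will be evaluated by one way repeated measure ANOVA with Bonferroni correction or Dunnet T3 correction". The protocol has no statistical section that adds to this.

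**The concern.** The between-arm sentence leaves three things open: which of the three visits is tested, whether the outcome is the follow-up value or the change from baseline, and whether baseline enters the model. As worded, arm is the only factor. The repeated-measures sentence does not fill the gap. It is one-way and concerns each therapy, so it has a single within-patient factor and no arm-by-visit term. A significant change in one arm but not in another is not a test between arms.

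With 10 patients per arm this matters in two ways. Variation that baseline could explain stays in the error term, and chance differences at baseline carry through to the comparison. In addition, the choice of visit and of outcome form can still be made after the data are seen.

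**Working it through.** The documents give no power calculation, alpha, SD, effect size, dropout rate or baseline-to-follow-up correlation, so there is no figure of the plan's own to reproduce. The size is worked out over a range.

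**Inputs.** From the protocol: 3 arms of 10. Assumed: alpha 0.05; SD 1 at baseline and follow-up; bivariate normal values; no dropout; one arm shifted by 1 SD; enrolment order unrelated to baseline, so that allocation by patient number behaves like random allocation; r = 0.2, 0.3, 0.5, 0.7, 0.8.

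**Overall test.** The noncentrality for ANOVA on follow-up values is n × Σ(μ_j − μ̄)² / σ² = 10 × (1/9 + 1/9 + 4/9) = 6.67, with error df 30 − 3 = 27.
- Change scores have variance 2(1 − r), so the noncentrality is 6.67 / [2(1 − r)], with 27 df.
- ANCOVA has residual variance 1 − r². Chance baseline imbalance inflates it by about 1 + 1/25 = 1.04. The noncentrality is 6.67 / [1.04(1 − r²)], with 26 df. At r = 0.5 this is 6.67 / (1.04 × 0.75) = 8.55.

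Power (%) from the noncentral F distribution; simulation agrees within 1 point:

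| r | Follow-up ANOVA | Change ANOVA | ANCOVA | Gain over follow-up | Gain over change |
|---|---|---|---|---|---|
| 0.2 | 58.1 | 39.0 | 58.0 | −0.1 | 19.0 |
| 0.3 | 58.1 | 43.9 | 60.4 | 2.3 | 16.5 |
| 0.5 | 58.1 | 58.1 | 69.4 | 11.3 | 11.3 |
| 0.7 | 58.1 | 81.2 | 85.8 | 27.7 | 4.6 |
| 0.8 | 58.1 | 94.2 | 95.5 | 37.4 | 1.3 |

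**Any pairwise difference found** (simulated, same r values). The SAP's full rule (F test, then Levene, then Bonferroni or Dunnett T3) gives 54% throughout on follow-up values and 35/41/53/77/92% on change. ANCOVA contrasts with robust standard errors and Bonferroni give 53/55/64/81/93%.

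**Chance imbalance.** The baseline difference between two arms of 10 has a standard error of √(2/10) = 0.45 SD. The largest gap among the three arms exceeds 0.5 SD in about 50% of allocations. With no treatment effect, false positives at the five r values are:
- follow-up ANOVA: 5.4/5.8/7.0/8.7/9.5% in that half and 4.5/4.2/2.9/1.2/0.5% in the other;
- change ANOVA: 8.2/7.8/7.0/6.3/5.8% and 1.7/2.1/2.9/3.5/4.0%;
- ANCOVA: about 5% in both halves.

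Over all allocations each test gives about 5%.

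**LDL-C.** Patients are selected above 100 mg/dl and must be statin-naive (sections 4.2.1 and 4.2.2), which can lower r. If the entry cut lies at the population mean (assumed), the baseline variance shrinks to s² = 1 − 2/π = 0.363, and r in the trial becomes rs / √(r²s² + 1 − r²). An r of 0.3/0.5/0.7 before selection becomes 0.19/0.33/0.51. The simulated gain over follow-up values is then 0/3/12 points.

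**Skewed markers.** For an assumed lognormal marker (log-SD 0.8, r = 0.5, shift of 1 log-SD), power is 48% for raw ANOVA, 58% for log-scale ANOVA and 69% for log-scale ANCOVA. About half of that gain comes from the log scale.

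**Unequal variances.** Family-wise error with residual SDs of 1:1:3 is 3.4–4.3% under the SAP's rule, 6.2–6.8% for ANCOVA with a pooled standard error and Bonferroni alone, and 4.2–4.8% with HC2 standard errors and Satterthwaite degrees of freedom.

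**Open visit.** If each of the three visits is tested at 0.05, the chance of at least one false-positive overall test per marker is 1 − 0.95³ = 14.3% with independent visits. By simulation it is 12.9% or 10.1% at a between-visit correlation of 0.5 or 0.8.

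**The case against.** The best defence is that nothing here is invalid. The stated test has its nominal error on average, and the raised rates in imbalanced allocations are offset in the others. That stands: this is a point about efficiency and pre-specification, not bias. It is also true that the documents do not fix r, so the gain could be nothing or large. But an unknown r argues for ANCOVA, because follow-up values lose much when r is high and change scores lose much when r is low.

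The repeated-measures sentence mentions Dunnett T3, a between-group procedure, so it may have been meant to compare arms. If so, the wording still has to change, because a one-way model cannot do that.

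Objective 2 does list the visits, and testing at each is a natural reading. That reading brings the 10–14% error per marker shown above, and no visit is marked as the main one.

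Separate ANCOVAs by visit do not supply an arm-by-visit term. A mixed model with baseline, arm, visit and arm-by-visit would, and it is a reasonable alternative. The case for baseline adjustment does not depend on that choice. The figures also assume that no patient misses the visit.

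Finally, the robust standard errors may look like much machinery for 30 patients. The SAP already guards against unequal variances, however, and a pooled ANCOVA would remove that guard.

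**Conclusion.** The concern holds. The SAP's stated between-regimen test leaves visit and outcome form open and ignores a baseline that is measured for every marker with a stated schedule. It should be changed, though the analysis as written is not invalid.

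Under the assumptions listed, adjusting for baseline gains between nothing (r = 0.2) and about 37 points of power (r = 0.8) over follow-up values, and between 19 points and 1 point over change scores. The gain over follow-up values is material only at r of about 0.5 or more, and the gain over change scores only at r of about 0.5 or less. For LDL-C the gain over follow-up values may be close to nil. The reading of the SAP is secure; the size of the loss cannot be settled from the documents.

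**What to change.** Replace the between-arm one-way ANOVA by ANCOVA for each marker, with arm as factor and the patient's own baseline value as covariate.
- **Visit.** Name one follow-up visit in advance. Month 12, the last scheduled, is a natural choice. Use the same model at the other two visits as secondary.
- **Outcome form.** If change scores were intended, say so and still include the baseline covariate. Name in advance the skewed markers to be log-transformed at both baseline and follow-up.
- **Contrasts.** Report the three adjusted arm differences with Bonferroni-adjusted 95% intervals, that is 1 − 0.05/3 = 98.3% per contrast.
- **Unequal variances.** In place of the Levene and Dunnett T3 rule, use HC2 standard errors with Satterthwaite degrees of freedom for all three contrasts, without a pre-test.
- **Software.** The SAP states: "Statistical analysis will be performed by using SPSS for Windows, version 20.0". Check that this version offers the method, or name software that does.
- **Within-arm tests.** Label the repeated-measures results descriptive, and read the regimen comparison from the contrasts.

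The change needs no new visits, samples or patients, only SAP wording. ANCOVA leaves 26 error degrees of freedom instead of 27, which costs about 2 points of power if r = 0 (58% to 56%). The robust standard errors cost a further 1 to 2 points if variances are equal (65.5% to 63.7% at r = 0.5).

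### The SAP tests differences in medians between the three arms with one-way ANOVA, which compares means, and names no method for skewed markers in any group comparison

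*SAP*

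**What the plan says.** The SAP is short and has no numbered sections. Its statements on this point are:

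- **Summaries.** "All results will be expressed as mean values (mean SD) or median values (median and range"). Reporting by medians is therefore foreseen.
- **Patients versus controls.** "ANOVA one-way statistical analysis or by Student's t-test (with Kolmogorov-Smirnov for normality"). A normality check is named, but not what follows if it fails.
- **Change over time.** "The statistical differences in the effect of each therapy on laboratory mean values" are to be assessed by one-way repeated-measures ANOVA.
- **Three arms.** "To compare the differences in the median values of laboratory tests between 3 groups, ANOVA one-way will be applied". Pairwise follow-up is chosen by a variance check: "with Bonferroni if Levene test ≥ 0.05 or Dunnet T3 if Levene test < 0.05".
- **Correlation.** "Correlation analysis between variables will be performed by Pearson's correlation or Spearman's correlation as appropriate".

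In the Protocol, objective 2 (section 3) is "To compare the effect of lipid-lowering regimes" on lipids, oxidative stress, tryptophan metabolism, renal measures and side effects. Section 4.6 gives 10 patients per arm. Section 5 lists the markers, among them "Serum concentrations of Oxidative stress indices (MDA, All/UA, Taurine), Trp degradation indices (Kyn, Trp, Kyn/Trp ratio"), together with lipids, CK, transaminases and urine protein. The Protocol has no statistical section that adds a method.

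**The concern.** The three-arm sentence names one quantity and tests another. One-way ANOVA, Bonferroni comparisons and Dunnett T3 all concern means. As written, a results table could show medians and ranges beside p-values that refer to means.

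The sentence also carries a lot of weight. It is the SAP's only clear comparison of the three regimens with each other, so objective 2 rests on it. The markers are positive quantities and some are ratios (Kyn/Trp, All/UA), a type of measurement that may be right-skewed. With 10 per arm, a few large values can inflate the within-group variance and hide a difference that a log-scale or rank analysis would find.

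**Working it through.** **1. Does any sentence supply a method for skewed markers in a group comparison?**

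| SAP element | What it addresses | Closes the gap? |
|---|---|---|
| Kolmogorov-Smirnov | Normality check, patients versus controls only | No, no consequence is stated |
| Levene, then Bonferroni or Dunnett T3 | Unequal variances | No, both procedures compare means |
| Conditional wording in the repeated-measures sentence | Choice of multiplicity correction | No |
| Spearman | Correlation | No, not a group comparison |

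No rank test and no transformation is named for any group comparison.

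**2. Mean and median are different targets under skew.** For a lognormal marker with log-mean m and log-SD s, the median is exp(m) and the mean is exp(m + s²/2). With equal medians and log-SDs of 0.3, 0.3 and 1.0, the third mean exceeds the others by exp((1.0² − 0.3²)/2) = exp(0.455) = 1.58-fold.

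**3. What does the mismatch cost in power?** The documents give no power calculation, alpha, effect size or SD, so there is no planned figure to reproduce. Arm size (10) is from Protocol section 4.6. Assumed here: lognormal markers, the log-SDs and ratios shown, alpha 0.05. The lognormal assumption favours the log analysis. A halving is ln 2 = 0.693 on the log scale, which is 0.693/0.5 = 1.39 log-SDs or 0.693/0.8 = 0.87 log-SDs. A ratio of 0.7 at log-SD 0.3 is 0.357/0.3 = 1.19 log-SDs.

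Overall test, 40,000 simulated trials per row, percentage rejecting:

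| Log-SD | Medians | Raw ANOVA | Kruskal-Wallis | Log ANOVA |
|---|---|---|---|---|
| 0.3 | 1, 0.7, 0.7 | 74.0 | 70.0 | 74.0 |
| 0.5 | 1, 0.5, 0.5 | 84.4 | 83.6 | 86.5 |
| 0.5 | 1, 1, 0.5 | 75.1 | 83.4 | 86.5 |
| 0.8 | 1, 0.5, 0.5 | 37.2 | 42.1 | 45.6 |
| 0.8 | 1, 1, 0.5 | 26.2 | 42.0 | 45.5 |
| 0.8 | identical | 3.7 | 4.5 | 4.9 |

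**4. The SAP's full two-step rule.** The overall test must be significant, and then at least one pair, by Bonferroni if Levene p ≥ 0.05 and by Dunnett T3 otherwise. Percentage succeeding:

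| Log-SD | Medians | Raw | Kruskal-Wallis + Dunn | Log |
|---|---|---|---|---|
| 0.5 | 1, 1, 0.5 | 69.5 | 79.9 | 83.5 |
| 0.5 | 1, 0.5, 0.5 | 72.3 | 79.6 | 83.4 |
| 0.8 | 1, 1, 0.5 | 18.5 | 37.4 | 41.3 |
| 0.8 | 1, 0.5, 0.5 | 21.6 | 38.0 | 41.8 |

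**5. Skew alone.** Holding the effect at 1.25 log-SDs in one arm and varying only the skew (10,000 trials each), raw ANOVA power is 66%, 49%, 39% and 29% at log-SD 0.5, 0.8, 1.0 and 1.2. Kruskal-Wallis stays at 74% to 76% and log ANOVA at 78% to 79%.

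**6. False positives.** With identical skewed arms raw ANOVA is conservative (3.7%). With equal medians and log-SDs 0.3/0.3/1.0, raw ANOVA rejects in 11% of trials, against 8% for log ANOVA and 6% to 7% for Kruskal-Wallis. The means do differ in that case (step 2), and the full raw two-step rule names a pair in only 2.5%.

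**7. Could a normality test choose the method?** In samples of 10, a Kolmogorov-Smirnov test in Lilliefors form flagged lognormal data in 19%, 34% and 46% of samples at log-SD 0.5, 0.8 and 1.0. It would usually miss the skew.

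**The case against.** **One wrong word.** The two preceding SAP sentences speak of means, and the Levene, Bonferroni and Dunnett T3 sequence is coherent for means. A slip is plausible. Correcting it settles what the sentence tests, but markers reported as medians would then have no between-arm test at all.

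**The plan does consider non-normality.** It names Kolmogorov-Smirnov for patients versus controls. That is fair: there the gap is a missing consequence rather than a missing thought. The check is not attached to the three-arm comparison.

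**The repeated-measures sentence might also compare arms,** since it offers Dunnett T3, a between-group procedure. The wording is loose, but a one-way repeated-measures ANOVA has time as its only factor, so the within-therapy reading is the natural one.

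**The large losses need particular scenarios.** This stands. The tests are unaffected by rescaling, so one arm doubled is the same case as two arms halved, where the overall-test loss at log-SD 0.8 is 5 points (37% versus 42%). All three arms contain simvastatin, so smaller contrasts deserve equal display. With one arm shifted (8,000 trials each), raw ANOVA / Kruskal-Wallis / log ANOVA give 31/32/35% (log-SD 0.3, ratio 0.8), 25/30/33% (0.5, 0.7), 12/13/15% (0.5, 0.8), 9/14/15% (0.8, 0.7) and 6/8/9% (0.8, 0.8). Every method is weak there, and sample size is the tighter limit. The losses are smaller but run in the same direction.

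**Conclusion.** The concern holds and should be fixed. From the text alone it is certain that the SAP assigns tests of means to a difference in medians and gives no rank or transformed analysis for any group comparison.

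The numerical consequence is conditional on skew and effect pattern, neither of which the documents report. Under the lognormal assumption the overall-test difference against Kruskal-Wallis runs from none (log-SD 0.3, or log-SD 0.5 with two arms halved) to 16 points (log-SD 0.8, one arm halved). Under the full two-step rule it reaches about 19 points. Where skew is mild, the problem is mainly that the compared quantity is undefined. No false-positive inflation was found when the arms have identical distributions.

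**What to change.** Replace the three-arm sentence with text along these lines:

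> Before the data are analysed, each marker is listed once, with its summary measure and its test. Markers expected to be positive and skewed are compared between the 3 groups by one-way ANOVA on the log scale, with the planned Bonferroni or Dunnett T3 comparisons, and reported as geometric-mean ratios with 95% CI. Markers summarised by medians are compared by Kruskal-Wallis with Bonferroni-adjusted Dunn comparisons (Mann-Whitney for patients versus controls), described as tests of location or stochastic ordering. All other markers are compared by means with one-way ANOVA.

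Three additions would complete it:

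- State the matching method, log-scale or rank-based, for the within-therapy repeated measures.
- State whether the arms are compared on follow-up values or on change from baseline, and at which of the 4-, 8- and 12-month visits.
- State whether controls are matched individually. Mann-Whitney is unpaired, as is the Student's t-test already planned.

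Assign markers in advance rather than by a normality test, for the reason in step 7.

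The cost is one SAP paragraph and one marker list. Results for the affected markers are read as ratios or rank shifts instead of absolute differences, and Kruskal-Wallis gives up a little power where skew is mild (70% versus 74% at log-SD 0.3 with two arms at ratio 0.7).

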(1) Do different lipid-lowering drugs (simvastatin monotherapy and ezetimibe/simvastatin combination therapy) have a different impact on the lipid profile, oxidative stress indices, Tryptophan degradation?

(2) Does statin monotherapy or co-administration of ezetimibe ameliorate the renal dysfunction in CKD patients?

(3) How do lipid-lowering therapy effect on lipidemia disorders in patients with CKD by mechanism involved in oxidative stress and tryptophan?

(4) Are the unexpected effects on muscle problem and hepatic enzyme profile of long-term statin monotherapy and statin/ezetimibe combination therapy a big concern?

II. REVIEW OF RESEARCH LITERATURE

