2.12. Simvastatin

- Treat with statins for 1-2 weeks, up to 4-6 weeks, and maintain during long-term treatment.
- Simvastatin largely excreted in the feces. Approximately 10-15% of the drug excreted by the kidney
- Dosage is 5-80 mg/day, in the evening.
- No dosage adjustment is needed in the elderly
- **Contraindications of Simvastatin:**
 - + Active liver disease or unexplained persistent elevations of serum transaminases

- + Pregnancy and lactation
- + Concomitant administration of potent CYP3A4 inhibitors (e.g. itraconazole, ketoconazole, posaconazole, HIV protease inhibitors (e.g. nelfinavir), erythromycin, clarithromycin, telithromycin, and nefazodone)
- + Concomitant administration of gemfibrozil, ciclosporin, or danazol.
- **Unexpected effects of Simvastatin and how to manage unexpected effects**
 - + **Myopathy:** The risk of myopathy is related to dose. In a clinical trial of 41,413 patients treated with simvastatin, 24,747 patients (about 60%) with an average follow-up of at least 4 years, the incidence of myopathy was approximately 0.03%, 0.08% and 0, 61% at doses of 20, 40 and 80 mg/day, respectively.
 - If the patients have muscle aches, weakness or cramps, do CK test. If CK increases (> 5 times) discontinue treatment, re-assess levels within 5 to 7 days.
 - If the muscular symptoms are severe and cause daily discomfort, even if the CK levels are < 5 times normal, consider stopping treatment.
 - + **Elevated liver enzymes:** Continuous elevations (up to > 3 times) liver enzymes have occurred in some patients receiving simvastatin.
 - When simvastatin is discontinued, the level of transaminase usually decreases gradually down to the pre-treatment level.

+ **Diabetes Mellitus**

Some evidence suggests that statins as a class raise blood glucose and in some patients, at high risk of future diabetes, may produce a level of hyperglycemia where formal diabetes care is appropriate. This risk, however, is outweighed by the reduction in vascular risk with statins and therefore should not be a reason for stopping statin treatment.

+ Other side effects: Dizziness, fainting, fast or irregular heartbeat,...

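### Side effects are a stated objective, but the SAP plans no per-arm count of patients with marked CK or transaminase elevations, muscle pain or serious adverse events

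*SAP*

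**What the plan says.** The protocol raises side effects twice. Research question 4 (section I) asks: "Are the unexpected effects on muscle problem and hepatic enzyme profile of long-term statin monotherapy and statin/ezetimibe combination therapy a big concern". Objective 2 (section 3) compares the three regimens on several outcomes, ending with "Tryptophan degradation, renal parameter, and side effect in Vietnamese CKD patient".

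The literature review (section 2.12) describes these effects patient by patient. For CK it says: "If CK increases (> 5 times) discontinue treatment, re-assess levels within 5 to 7 days". For the liver it says: "Continuous elevations (up to > 3 times) liver enzymes have occurred in some patients receiving simvastatin".

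Section 4.6 has muscle pain recorded at each follow-up, and serious adverse events asked of patients who do not attend. Section 5 has CK, SGOT and SGPT measured at baseline and at 4, 8 and 12 months.

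The SAP is one page. It expresses all results as mean with SD or median with range. Change within each therapy is tested by repeated-measures ANOVA on laboratory means. For the comparison of regimens it says: "To compare the differences in the median values of laboratory tests between 3 groups, ANOVA one-way will be applied". Pairwise tests (Bonferroni or Dunnett T3, chosen by the Levene test) follow only if the three-group test is significant. The rest is the comparison of patients with controls, and correlations. No count, proportion, patient listing or safety table is planned.

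**The concern.** Whether side effects are a concern is a question about how many patients had one. Muscle pain is a yes/no item, and neither a mean nor a median is a usable summary of it. Serious adverse events have no planned summary at all. For CK and the transaminases the planned test compares arm means (ANOVA tests means, although the SAP sentence speaks of medians). A mean over 10 patients responds poorly to one or two very high values, because those values also inflate the within-arm variance that the F test divides by.

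At stake is how the result can be read. If the report has only non-significant mean comparisons, nothing in it shows whether no patient, one or two had a marked elevation, or how large a risk 10 patients per arm leave open.

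**Working it through.** **Inputs.** "30 enrolled patients will be randomized into 3 groups", 10 in each (section 4.6). The one-way ANOVA then has 2 and 27 degrees of freedom. The SAP states no significance level for treatment comparisons; 0.05 two-sided is assumed. Neither document gives a power calculation, effect size or SD, so there is no design figure to reproduce.

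**Step 1: limiting F.** Let k of the 10 patients in one arm have an extreme value M and all other patients 0. This is the limit as the elevation grows relative to ordinary variation.

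- Between-group sum of squares: 10 × [(kM/10 − kM/30)² + 2 × (kM/30)²] = k²M²/15
- Within-group sum of squares: k(10 − k)M²/10
- F = [(k²M²/15)/2] ÷ [(k(10 − k)M²/10)/27] = 9k/(10 − k)
- With 2 and 27 degrees of freedom, p = (1 + 2F/27)^(−13.5)

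M cancels, so F does not depend on how high the value goes. The last column is the exact three-group test on the counts k/10, 0/10, 0/10, with p = 3 × C(10,k)/C(30,k).

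| k in one arm | F | ANOVA p | Exact p on counts |
|---|---|---|---|
| 1 | 9/9 = 1.00 | 0.38 | 1.00 |
| 2 | 18/8 = 2.25 | 0.125 | 0.31 |
| 3 | 27/7 = 3.86 | 0.034 | 0.089 |
| 4 | 36/6 = 6.00 | 0.007 | 0.023 |

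**Step 2: with ordinary variation added.** 20,000 simulated trials per scenario. The distributions are assumptions, since the documents give none: lognormal CK with median 0.4 times the upper limit of normal (ULN) and log-SD 0.4 to 0.6; lognormal transaminase with median 0.6 times ULN and log-SD 0.4 to 0.5. Share of trials with ANOVA p < 0.05:

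| Affected patients in one arm | CK at 6 × ULN | Transaminase at 3.5 × ULN |
|---|---|---|
| 1 | 0 to 0.1% | 0.7 to 1.7% |
| 2 | 0.1 to 2.7% | 8 to 11% |
| 3 | 74 to 92% | 49 to 57% |

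With no affected patient, the CK comparison rejected in about 4 to 5% of trials. One very high CK therefore makes a significant result less likely than none would. With one patient at 6 times ULN, the arm mean is about 1.0 times ULN and the arm median 0.43 to 0.45, so neither summary points to a value above 5 times.

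**Step 3: what zero events would show.** The exact two-sided 95% upper limit for 0/n is 1 − 0.025^(1/n).

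- 0/10: 1 − 0.025^(1/10) = 30.8%
- 0/30: 1 − 0.025^(1/30) = 11.6%

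For comparison, the exact 95% interval is 0.3% to 44.5% for 1/10 and 2.5% to 55.6% for 2/10.

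**Step 4: timing.** Section 2.12 describes a CK test when muscle symptoms appear and a re-check within days. The scheduled samples are four months apart. A high CK from an unscheduled test may never enter the means at 4, 8 and 12 months.

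**The case against.** Several points on the other side stand.

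- **The SAP is not limited to means.** It allows median with range, and a range would display a very high CK. A reader might infer that affected patients would be invisible; the text does not support that. But the range is one of two options, and it gives one maximum per arm, not a number of patients.
- **The levels are not study limits.** Section 2.12 is literature review. Its CK figure is a management trigger, and its enzyme figure only describes what has been seen, as sustained elevation. A reader might take more than 3 times as the protocol's own transaminase limit; it is not stated as one.
- **Counts are no more powerful.** In Step 1 the exact p on counts is larger than the ANOVA p in every row. Most of the non-significance comes from 10 patients per arm. A reader might infer that a test on counts would find what ANOVA misses; it would not. The case for counts is descriptive.
- **The insensitivity is not general.** Three affected patients in one arm would usually be detected for CK, and about half the time for a transaminase.
- **No passage says a null result will be reported as safety.** That is a risk left open by the plan, not something it states. Comparing enzyme values between groups is also a legitimate, if incomplete, answer to a question about the enzyme profile.

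It is also tempting to quantify the risk from the rates in section 2.12: "the incidence of myopathy was approximately 0.03%, 0.08% and 0, 61% at doses of 20, 40 and 80 mg/day, respectively". Applied as they stand, they give 1 − (1 − 0.0008)^20 × (1 − 0.0003)^10 = 1.9% for any case among the 30 patients. But they come from an average follow-up of at least 4 years, and this trial lasts 12 months. Assuming a constant rate over 4 years, the chance is 1 − (1 − 0.0002)^20 × (1 − 0.000075)^10, about 0.5%. They are also simvastatin myopathy rates, not rates of CK above 5 times, so the conclusion does not rest on them.

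What the objections leave untouched is the omission itself: no number of affected patients per arm is planned for any side effect.

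**Conclusion.** The concern holds as a missing descriptive analysis for a stated objective. Muscle pain and serious adverse events have no usable analysis, and marked CK or transaminase elevations are not counted. One or two such elevations in an arm would normally leave the planned comparison non-significant (limiting p = 0.38 and 0.125), so that result cannot stand as evidence of safety.

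The limiting F values need only 10 patients per arm and elevations confined to one arm. The simulated rates also rest on the assumed distributions, and calling a result non-significant rests on the assumed 0.05 level. It does not follow that the plan conceals affected patients entirely, or that another test would rescue a formal safety comparison at this sample size.

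**What to change.** Add one safety table to the SAP. For each arm, give the number and percentage of patients, with exact 95% confidence interval and stated denominator, who have:

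- a worst follow-up CK above 5 times the laboratory's upper limit of normal, unscheduled tests included;
- a worst follow-up SGOT or SGPT above 3 times that limit, unscheduled tests included;
- unexplained muscle pain at any follow-up;
- any serious adverse event.

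State that the two laboratory levels are taken from section 2.12 for reporting only and imply no treatment rule.

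Restate the side-effect part of Objective 2 as descriptive. Note that no events in an arm of 10 leaves an upper limit of 30.8%, and none in 30 leaves 11.6%. Add that a non-significant comparison of mean CK or enzymes will not be reported as absence of a safety difference. Do not present the counts as a gain in power.

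**Cost.** One table and a few sentences. CK, SGOT, SGPT and muscle pain are already collected. Section 4.6 mentions asking about serious adverse events only for patients who miss visits, so the protocol should say whether attenders are asked too; otherwise that row must carry the limitation. The safety claim becomes more modest.
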